6.8 Pharmacokinetic/Pharmacodynamic Analysis

Not Applicable.

6.9 Quality-of-Life Analysis

Not Applicable.

6.10 Pharmacoeconomic Analysis

Not Applicable.

6.11 Other Outcomes

Not Applicable.

6.12 Safety Analysis

Safety will be assessed by evaluating the incidence of adverse events including cardiovascular adverse events such as predefined MACE composite, and evaluating ECGs; laboratory tests and vital signs. A CV Endpoints Committee blinded to treatment assignment will adjudicate potential cardiovascular adverse events and each death to determine if it meets MACE criteria. The procedures and rules of adjudication of these events by the CV Endpoints Committee is described in a separate charter.

For the primary, secondary, and additional safety endpoints, time to event will be the time from the date of randomization or the date of last dose of study medication to the date of first occurrence of any event in the respective endpoint. If a subject reports an event for a given safety endpoint after treatment discontinuation, the reported event will be counted toward the treatment to which they were randomized. Subjects who are lost to follow-up during the study or who do not exhibit an episode of an event for the specific safety endpoint throughout the study will be censored at the day of last contact.

All safety endpoints will be analyzed using the Full Analysis Set (FAS). The FAS will consist of all subjects who were randomized and received at least one dose of double-blind study medication. Non-inferiority will be assessed only for the primary safety endpoint.

6.12.1 Primary Safety Endpoint

The primary safety variable is the time from randomization to the first occurrence of any event in the predefined MACE composite. The goal of the primary safety analysis is to compare the risk of a predefined MACE during treatment with febuxostat to that of allopurinol.

Survival analysis using the Cox Proportional Hazards (CPH) model will be fitted on the time to the first occurrence of any event in the predefined MACE composite. The hazard ratio (febuxostat versus allopurinol) for the primary safety endpoint will be computed based on febuxostat and allopurinol estimated hazard rates. The febuxostat treatment group will be compared to the allopurinol treatment group to test for non-inferiority in the MACE composite rate using a CPH model with treatment as factor in the model and baseline renal function as a stratification factor. Non-inferiority of febuxostat to allopurinol will be declared (at an interim or at the final analysis) if the current upper 1-sided CI for the hazard ratio calculated with critical values obtained using the Lan-DeMets-O'Brien-Fleming alpha spending function, which preserves an overall 1-sided false-rejection rate of 2.5%, is less than 1.3.

Kaplan-Meier plot for the time to first occurrence of any event in the adjudicated MACE composite will be produced by treatment group (overall and within the levels of the stratification factor, baseline renal function).

A sensitivity analysis on the primary safety endpoint will also be performed by excluding MACE that occur more than 30 days after treatment discontinuation.

Assessment of the proportional hazards assumption will be made by inspection of the Kaplan-Meier curves and using plots of Schoenfeld residuals. In the Kaplan-Meier curves, if the proportional hazard assumption is satisfied then the graph of the survival function versus the survival time should result in a graph with parallel curves. In the plots of Schoenfeld residuals, if the proportional hazard assumption is satisfied then the graph of the Schoenfeld residuals obtained from the primary CPH model versus the ordered time of events along with smoothing spline should result in a horizontal line.

Alternative methods of analysis may be considered should some of the underlying model assumptions seem inappropriate (e.g., non-proportional hazards). The reasons for any changes to the planned approach and methods will be fully documented.

An additional analysis on the primary safety endpoint will be performed using Cox-proportional hazards model controlling for the effect of NSAIDs use. The model will include treatment group, baseline renal function, and use of NSAIDs as explanatory variables. A similar analysis will control for the effect of low-dose aspirin use.

To identify risk factors an additional exploratory analysis on the primary safety endpoint will be performed using multivariate CPH modeling. The multivariate model will include treatment group and the following covariates jointly in the model with baseline renal function as the stratification factor: age, gender, BMI, NSAIDs use, low-dose aspirin use, smoking history,

baseline sUA, and history of diabetes, hypertension, non-fatal MI, or non-fatal stroke. No interaction terms will be introduced in the multivariate model. The backward elimination technique with a significance level to stay (SLS) in the model of SLS = 0.05 will be implemented for variable selection while always retaining treatment group and baseline renal function as stratification factor in the model.

In addition, the number and percentage of subjects with predefined MACE will be summarized within the levels of each subgroup variable. The relative risk (febuxostat versus allopurinol) and 95% CI based on the normal approximation will be calculated within the levels of each subgroup variable. Homogeneity among the levels of the subgroup variables will be assessed using the Cochran-Mantel-Haenszel test. A forest plot indicating the point and 95% CI estimates of the risk ratios within the levels of each subgroup variable will also be presented.

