3.2 Study Design

This is a phase 3B multicenter, randomized, double-blind, active-controlled study designed to evaluate the CV safety of febuxostat compared with allopurinol in subjects with gout and significant CV comorbidities. Approximately 7500 subjects will be randomly assigned to study drug treatment.

The overall duration of the study is dependent on the number of predefined MACE. The length of the study is expected to be approximately 9 years. The length of study participation for each subject will vary due to the event driven study design. This study is designed to have a maximum of 624 MACE.

On Study Day 1, eligible subjects will be randomized in a 1:1 ratio to receive either febuxostat once daily (QD) or allopurinol QD. Randomization will be stratified based on baseline renal function (normal renal function or mild renal impairment versus moderate renal impairment). Baseline renal function will be defined using the following criteria based on estimated creatinine clearance (eCLcr):

- Normal renal function: defined as an eCLcr ≥ 90 mL/min.
- Mild renal impairment: defined as an eCLcr 60 to 89 mL/min, inclusive.
- Moderate renal impairment: defined as an eCLcr 30 to 59 mL/min, inclusive.

where estimated creatinine clearance (eCLcr) is calculated using the Cockcroft-Gault formula corrected for ideal body weight (IBW); IBW is 50 kg for males and 45.5 kg for women, plus 2.3 kg for each inch in height >5 feet (60 inches)]:

[figure not shown]
$$eCLcr = \frac{(140 - \text{Age}[\text{yr}]) \times (\text{IBW}[\text{kg}]) (\text{women multiply by } 0.85)}{72 \times (\text{serum creatinine} [\text{mg/dL}])}$$

Subjects randomized to febuxostat will initially receive the 40 mg dose QD. Subjects will remain on 40 mg for the remainder of the study if their serum uric acid (sUA) is <6.0 mg/dL at the Week 2 Visit. If their sUA is ≥ 6.0 mg/dL at the Week 2 Visit they will receive febuxostat 80 mg QD at the Week 4 visit, and will remain on this dose for the remainder of the study.

Subjects randomized to allopurinol who have normal renal function or mild renal impairment will initially receive allopurinol 300 mg QD with the dose increased in 100 mg increments monthly until either a sUA <6.0 mg/dL or an allopurinol dose of 600 mg QD is achieved. Subjects randomized to allopurinol who have moderate renal impairment will initially receive allopurinol 200 mg QD with the dose increased in 100 mg increments monthly until either a sUA

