5.0 DETERMINATION OF SAMPLE SIZE

A total of 7500 subjects (3750 per treatment group) are planned to be enrolled in this study. The sample size will provide at least 90% power to meet a non-inferiority margin of 1.3 for the hazard ratio (febuxostat relative to allopurinol) of the primary endpoint. The sample size calculation assumed a true hazard ratio of 1.0 at a 1-sided 2.5% significance level with 3 interim analyses at approximately 25%, 50% and 75% of the events based on critical values obtained using the Lan-DeMets - O'Brien-Fleming alpha spending function.

For the determination of non-inferiority between the febuxostat treatment group and the allopurinol treatment group, the sample size calculation further assumed:

- Constant proportional hazards and exponential survival curves,
- Annual adjudicated MACE composite rate of 2.8%,
- Maximum length of participation of 5 years,
- Accrual time of 2.5 years, and
- Annual drop-out rate of 10%.

This study is designed to have a maximum of 624 MACE.

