6.13 Interim Analysis

This study is designed to have a maximum of 624 MACE composite events for assessing non-inferiority of febuxostat relative to allopurinol with regard to cardiovascular risk assuming a true hazard ratio of 1.0 and 90% power. Interim analyses will be conducted when approximately 25%, 50% and 75% of the events or equivalently approximately 156, 312, and 468 events have occurred, followed by a final analysis. In this group sequential trial with 4 equally-spaced analyses and a one-sided overall significance level of 0.025, the Lan-DeMets alpha spending approach with an O’Brien-Fleming stopping boundary will be used. Table 6.c displays the projected critical boundaries and the overall 1-sided 2.5% significance level spending at each interim analysis obtained from the O’Brien-Fleming spending function. [contact] was used to determine the critical boundaries.

Table 6.c O’Brien-Fleming Spending Function

Interim Look	Information Fraction	Critical Boundary	Alpha Spending at Each Interim	Cumulative Alpha Spending
1	156/624 = 0.25	4.333	0.000	0.000
2	312/624 = 0.50	2.963	0.002	0.002
3	468/624 = 0.75	2.359	0.008	0.010
4	624/624 = 1.00	2.014	0.015	0.025

Therefore, at the 3 interim and at the final analyses, one-sided confidence intervals for the hazard ratio of febuxostat relative to allopurinol for the primary endpoint will be constructed using critical values obtained using the Lan-DeMets -O’Brien-Fleming alpha spending function. At each analysis, if the upper confidence limit of the hazard ratio is ≤ 1.3 , the study will be stopped and the non-inferiority of febuxostat relative to allopurinol with regard to cardiovascular risk will be declared. If non-inferiority is declared at an interim analysis, subsequent analyses of the primary endpoint will be considered sensitivity analyses.

Periodically during the course of the study, a blinded assessment of the annual adjudicated MACE rate will be made. The number of subjects planned to be enrolled in this study was based

on an event rate of 2.8%, which was based on limited information. Based on the overall blinded MACE rate observed, an assessment will be made to determine whether or not to adjust the number of subjects planned for enrollment.

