At the DMC meeting on ^{PPD} [REDACTED], the 75% interim analysis results based on 468 adjudicated MACE for the primary MACE endpoint to assess cardiovascular safety was reviewed by the DMC. At the DMC meeting on ^{PPD} [REDACTED], the DMC informed Takeda that the non-inferiority criterion for the primary endpoint was met at the 75% interim analysis conducted in ^{PPD} [REDACTED]. According to the study design, the study should have been stopped and the non-inferiority of febuxostat relative to allopurinol with regard to cardiovascular risk should have been declared. However the DMC recommendation was to continue the trial without modification until the maximum 624 unique events were achieved to further assess all cause mortality (which was not a protocol specified endpoint) and CV mortality (which is specified only as a component of the MACE endpoint). Takeda agreed to follow the DMC recommendation and continue the study.

Based on the group sequential design, the 75% interim analysis will be the primary analysis for the primary MACE endpoint for the purpose of statistical inference. The continuation of the study to protocol-specified maximum events (624 unique MACE) is for the assessment of all cause mortality and CV mortality. The analyses of all cause mortality and CV mortality with and without death events after discontinuation of treatments will be added to the end of study analysis. An updated sensitivity analysis for the primary MACE endpoint based on 624 unique MACE will also be conducted to provide additional supportive evidence for the primary endpoint.

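### The primary MACE estimate comes from the 468-event look with no correction for sequential stopping, and the 624-event hazard ratio ranks only as a sensitivity analysis

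*SAP*

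**What the plan says.** SAP section 5.0 sets the sample size to "meet a non-inferiority margin of 1.3 for the hazard ratio (febuxostat relative to allopurinol) of the primary endpoint", with 90% power at a true hazard ratio of 1.0, a one-sided 2.5% level and three interim looks. Table 6.c gives the looks at 156, 312, 468 and 624 events, with critical values 4.333, 2.963, 2.359 and 2.014.

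Section 6.12.1 describes the estimate: "The hazard ratio (febuxostat versus allopurinol) for the primary safety endpoint will be computed based on febuxostat and allopurinol estimated hazard rates". The model is a Cox model stratified by baseline renal function. The decision rule is that non-inferiority "will be declared (at an interim or at the final analysis) if the current upper 1-sided CI for the hazard ratio", using the spending-function critical value, is below 1.3.

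Section 6.13 states the general rule that, once non-inferiority has been declared at an interim, "subsequent analyses of the primary endpoint will be considered sensitivity analyses". It then records that the criterion was met at 468 events, that the trial continued to 624 on the DMC's recommendation in order to assess mortality, and that "the 75% interim analysis will be the primary analysis for the primary MACE endpoint for the purpose of statistical inference". The 624-event MACE result is to be an updated sensitivity analysis giving supportive evidence.

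The sequential design enters the confidence limit. Nowhere does the SAP plan a point estimate that allows for the look having been selected by its own result.

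**The concern.** Alpha spending protects the test but does not make the estimate at the crossing look neutral. That look becomes primary only because its hazard ratio was low enough to cross, so the estimate is cut off from above. In a cardiovascular safety trial this pulls the estimate towards febuxostat, and the pull is larger when the true hazard ratio is higher.

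Usually little can be done, because the trial stops. Here it went on, and the full data hold a third more events (156 on top of 468). The plan ranks the estimate from those data below the one that is both less precise and more affected by selection.

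**Working it through.** **Inputs.** Margin 1.3, true hazard ratio 1.0, one-sided 0.025 and power 90% (SAP 5.0); 1:1 allocation (3.2); event counts and critical values (Table 6.c). Assumption: the variance of the log hazard ratio with d events is 4/d, which is its value when events are split equally between the arms.

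**Reproducing the design.** Recursive integration with the Lan-DeMets O'Brien-Fleming spending function returns boundaries 4.333, 2.963, 2.359 and 2.014. The stated values give a total one-sided error of 0.0250 and power of 0.901 at 624 events. The plan's own figures therefore hold.

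**Cap on the estimate.** Crossing with d events and critical value c requires ln HR + 2c/√d < ln 1.3, so HR < 1.3 × exp(−2c/√d). At the third look, 1.3 × exp(−2 × 2.359/√468) = 1.3 × exp(−0.2181) = 1.045. An unequal split of events raises the variance and lowers this slightly.

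**Bias given first crossing at the third look.** Trials were simulated in four increments of 156 events with the Table 6.c boundaries. The table shows geometric-mean hazard ratios.

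| True HR | Probability of first crossing at look 3 | HR at 468 events | Same trials, 624 events | Median-unbiased HR at 468 events |
|---|---|---|---|---|
| 1.00 | 43% | 0.981 | 0.986 | 0.992 |
| 1.10 | 23% | 0.999 | 1.023 | 1.005 |
| 1.20 | 6% | 1.010 | 1.054 | 1.014 |

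The 624-event column can be checked by hand. The last 156 events are unselected and carry a quarter of the information, so the expected log hazard ratio is 0.75 × (look-3 mean) + 0.25 × (truth). For a true value of 1.10: 0.75 × ln 0.999 + 0.25 × ln 1.10 = −0.0008 + 0.0238 = 0.0231, and exp(0.0231) = 1.023. Carrying on to 624 therefore removes a quarter of the look-conditional bias on the log scale, whatever the truth.

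Averaged over all stopping looks at a true value of 1.00, the naive estimate is 0.979, again about 2% low.

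**Median-unbiased estimate (stagewise ordering) at look 3.** Naive values of 0.90, 0.95, 0.98, 1.00, 1.02 and 1.04 become 0.940, 0.965, 0.987, 1.004, 1.022 and 1.041. The correction is negligible near the cap and material further below it.

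**Precision.** Repeated-limit half-widths on the log scale:
- 468 events: 2.359 × 2/√468 = 0.218
- 624 events: 2.014 × 2/√624 = 0.161

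The ratio is 1.35. It splits into a standard-error ratio of √(624/468) = 1.155 (0.0925 against 0.0801) and a critical-value ratio of 2.359/2.014 = 1.171. Slightly more than half of the widening thus comes from the boundary constant rather than from fewer events. For an observed hazard ratio of 1.00 the upper limits are exp(0.2181) = 1.244 and exp(0.1612) = 1.175.

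**The case against.** In a group-sequential design the first crossing is the primary analysis, and section 6.13 says so as a general rule. Section 6.14.2 places that clarification in Amendment 2, while section 6.14.3 attributes only Amendment 3 to the un-blinded team. Amendment 3 applies the rule. Replacing the primary estimate now, on the authority of people who know the 75% result, would carry its own cost in credibility. This stands, and it is why the 468-event look should remain primary.

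The size is also modest: about 2% at the design value. The larger gaps need a true hazard ratio of 1.10 to 1.20, where a first crossing at this look is less likely. That stands too.

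Third, the wording makes the look primary for statistical inference and names no single estimate to be quoted, and the 624-event analysis is promised. So the result is ranked lower but not withheld. This limits the point without removing it: the primary analysis yields the hazard ratio that readers will take as the main one, and no stopping-adjusted version is planned beside it.

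A reader might infer that a median-unbiased estimate would clear the bias left after 624 events. It would not. It is median-unbiased over the whole design, not given the look. At a true value of 1.10 it moves the look-3 mean only from 0.999 to 1.005.

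**Conclusion.** The point holds as a modest matter of estimation and reporting. The 468-event hazard ratio cannot exceed about 1.045. Given first crossing at that look it is about 2% low at a true value of 1.00, and further from the truth if febuxostat is harmful. The 624-event estimate is less biased, with a standard error smaller by a factor of 1.155.

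The figures assume variance 4/d, proportional hazards, looks at exactly the planned counts and the Table 6.c boundaries. The observed hazard ratio is not in the SAP, so the bias in this particular trial cannot be stated.

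Three stronger readings are not supported:
- **The non-inferiority decision is unsound.** The error rate reproduces at 0.025.
- **The look was chosen because it was favourable.** It follows the SAP's general rule on interim declarations.
- **The hazard ratio is unadjusted in every sense.** The model is stratified by renal function and its limit uses the boundary value. Only the allowance for stopping in the point estimate is absent.

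**What to change.** In sections 6.12.1 and 6.13:
- Keep the 75% look as the primary analysis and label it the decision analysis for non-inferiority.
- Beside its naive hazard ratio, report a stagewise-ordering median-unbiased hazard ratio, noting that it is median-unbiased over the whole design and not conditional on the look.
- Report the 624-event stratified Cox hazard ratio with its repeated one-sided limit (critical value 2.014, recomputed for the actual event counts) at equal prominence as the full-data estimate, without replacing the pre-specified primary analysis. Section 6.13 already foresees a spending-function limit at the final analysis, and repeated limits are valid at every look, so no alpha is spent.

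The cost is some SAP wording and a few lines of code, with no new data. The drawback for the sponsor is that the reported hazard ratio may be slightly less favourable.

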All subjects will return at Week 2 for measurement of sUA and all subjects will return for a Week 4 and Month 3 visit. If the Week 2 sUA level is <6.0 mg/dL, the subject will be dispensed study medication at Week 4, and the next visit will occur at Month 3. If the Week 2 sUA level is ≥ 6.0 mg/dL, the subject will be dispensed study medication at Week 4, and the next visit will occur at Week 6.

For the subset of subjects who have a Week 6 visit, if the Week 6 sUA level is <6.0 mg/dL, the subject will be dispensed study medication at Week 8, and the next visit will occur at Month 3. If the Week 6 sUA level is ≥ 6.0 mg/dL, the subject will be dispensed study medication at Week 8 and the next visit will occur at Week 10.

For the subset of subjects who have a Week 10 visit, the subject will be dispensed study medication at the Month 3 visit. After the Month 3 visit, no further dose adjustments will be made. All subjects will have Month 3 and Month 6 visits.

Following the Month 6 visit, all subjects will have visits every 6 months for the duration of the study. In addition, subjects with moderate renal impairment (eCLcr <60 mL/min) and/or subjects who are elderly (≥ 65 years of age) will have visits at Month 9 and Month 15 to monitor liver function tests. Subjects who are withdrawn from study medication treatment but have not withdrawn consent will be followed via phone calls every 2 months until the end of the study or until the subject experiences a CV event that is positively adjudicated as a MACE.

A Data Monitoring Committee (DMC) will periodically review results obtained in the study, including results at 3 planned interim analyses. They will monitor the progress and the on-going safety of subjects enrolled into the study. An Independent CV Endpoints Committee will be established to prospectively review all suspected CV events using blinded data. A periodic review of all serious adverse events and specific CV adverse event terms will be performed by the Chair of the CV Endpoints Committee. The Chair, not the sponsor, will designate cases for comprehensive review by the CV Endpoints Committee. All investigational sites will be required to collect relevant clinical information required for adjudication of all deaths and potential CV serious adverse events (SAE).

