6.6 Study Drug Exposure and Compliance

Summaries of study drug exposure, study participation, and compliance will be presented by treatment group and based on the FAS. No inferential statistics will be presented.

A subject's extent of drug exposure will be calculated as the duration of treatment in the double-blind treatment period. Duration of study drug exposure in days will be defined as (date of last dose - date of first dose + 1). If the date of last dose is missing and a subject has discontinued from the study, then, for summary purposes, the last dose date will be estimated as the last drug dispense date plus the number of days in the dosing interval or date of last contact, whichever comes first. The study participation will begin on the day of randomization and end on the day of last contact. Duration of study participation in days will be defined as (date of last contact - date of randomization + 1). For subjects who report a MACE event after treatment discontinuation, the start date of the event will be used as the date of last contact.

Treatment duration and study participation will be summarized overall and by treatment group using descriptive statistics and subject counts at the intervals: Day 1 to Day 364 [Year 1], Day 365 to Day 728 [Year 2], Day 729 to Day 1092 [Year 3], Day 1093 to Day 1456 [Year 4], Day 1457 to Day 1820 [Year 5], Day 1821 to Day 2184 [Year 6], and \geq Day 2185 [\geq Year 6]. In addition, within each treatment group, the duration of treatment by each dose will be summarized.

Study drug compliance will be calculated and summarized with descriptive statistics and subject counts within compliance categories (<80%, 80–<90%, \geq 90%). Compliance (%) will be calculated as the number of capsules taken divided by two times the number of days on drug.

The number and percentage of subjects on the final dose and with dose adjustment from initial dosing will be summarized by treatment group. The final doses based on sUA response and by baseline renal function are summarized in [Figure 3.a](#).

The number and percentage of subjects with use of each type of prophylactic medication based on the initial dosing and dose adjustment from initial dosing will be summarized by treatment group. In addition, descriptive statistics on the total number of days (date of last dose - date of first dose + 1) of prophylactic dosing will be summarized by treatment group.

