6.12.3 Other Safety Endpoints

The following additional safety endpoints will also be assessed:

- The time from randomization to the first occurrence of any event in the pre-defined MACE composite plus any of the following events:

- Urgent Cerebral revascularization [non-elective].
- Hospitalized congestive heart failure (CHF).
- Arrhythmias not associated with ischemia.
- Venous and peripheral arterial thromboembolic events; eg, Deep Vein Thrombosis (DVT) and Pulmonary Embolism (PE).
- Transient Ischemic Attack (TIA).
- The time from randomization to the occurrence of all-cause death,
- The time from randomization to the occurrence of all-cause death during treatment (from randomization to last dose of study medication),
- The time from last dose of study medication to the occurrence of all-cause death,

Survival analysis using the CPH model will be performed for these additional endpoints. Parameter estimates and a 2-sided 95% CI for the hazard ratio will be computed.

Kaplan-Meier plots will also be presented by treatment group.

The following other additional safety analyses will also be performed:

- The number of subjects with first occurrence of predefined MACE that occur no more than 30 days after a subject's last dose of study drug and the associated incidence rate by 100 patient-years of exposure along with 95% confidence intervals will be summarized by treatment group. The 95% CIs will be calculated based on the Poisson distribution. For a given treatment total patient-years (PY) of exposure will be calculated by summing across all subjects the total number of days on the treatment and dividing by 365.

The same analysis will be performed for each component of the MACE composite.

- Mortality analyses for the overall and by CV and Non-CV cause. The total number deaths and the death rate with 95% CI will be presented. The 95% CIs for the death rate will be calculated based on the Binomial distribution using exact method.
- The number and percentage of subjects with first occurrence of a pre-defined MACE composite will be presented by number of days in the study.
- List of CV risk factors for subjects with a predefined MACE composite comprising diabetes, hypertension, hyperlipidemia, obesity, and smoking will be provided by treatment group. Listings include subject number, age, gender, baseline renal function, primary MACE component, disposition, primary reason for discontinuation if disposition is early term, and CV risk factors.

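### The 30-day on-treatment MACE sensitivity analysis drops late events but sets no matching censoring date, so unequal stopping of study drug biases its hazard ratio

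*SAP*

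**What the plan says.** SAP 6.12.1 specifies the analysis in one sentence: "A sensitivity analysis on the primary safety endpoint will also be performed by excluding MACE that occur more than 30 days after treatment discontinuation". No censoring date follows.

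Four other places bear on it:

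- **6.12 Safety Analysis.** Subjects lost to follow-up, or with no event "for the specific safety endpoint throughout the study will be censored at the day of last contact". This is the only censoring rule for the time-to-event safety endpoints.
- **3.2 Study Design.** Subjects taken off study medication who "have not withdrawn consent will be followed via phone calls every 2 months until the end of the study", or until an adjudicated MACE.
- **6.6 Study Drug Exposure and Compliance.** For subjects "who report a MACE event after treatment discontinuation, the start date of the event will be used as the date of last contact".
- **6.13 Interim Analysis.** Analyses of all-cause and CV mortality "with and without death events after discontinuation of treatments will be added to the end of study analysis". All-cause death during treatment has a window in 4.3 and 6.12.3 (randomization to last dose). CV death has none.

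SAP 6.12.3 also plans a MACE rate that counts events up to 30 days after the last dose. Its denominator comes from "summing across all subjects the total number of days on the treatment and dividing by 365".

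**The concern.** An on-treatment Cox analysis needs two matching rules: which events count, and until when a subject is at risk. The SAP gives only the first. With the general rule for the second, an event-free subject who stops drug in year 1 can remain in the risk set for years, although no MACE of theirs after last dose + 30 days could be counted. On the 6.6 definition of last contact, a subject whose late MACE is excluded also stays at risk until the date of that MACE.

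This off-drug time enlarges the denominator without being able to add to the numerator. If both arms accumulate it equally, it cancels. If one arm stops more, that arm's hazard is diluted more. SAP 6.4 plans a Fisher's exact test of discontinuation between arms, so the plan does not presume equal stopping.

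The primary analysis counts MACE after discontinuation. This is therefore the only planned Cox comparison of the MACE composite restricted to the time on drug, and a reader would use it to judge whether off-drug follow-up dilutes a difference. With unequal stopping it brings in a distortion of its own, and it could disagree with the 6.12.3 rates, whose denominator leaves off-drug time out.

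**Working it through.** **1. Inputs.** From SAP 5.0: MACE 2.8% per year, so λ = −ln(1 − 0.028) = 0.0284; drop-out 10% per year, so μ = −ln(0.9) = 0.105; accrual 2.5 years and maximum participation 5 years, so follow-up is uniform on 2.5–5 years. Because Table 6.a runs to Month 84, follow-up of 2.5–7 years is also used. The rate of stopping drug in each arm, and the share of discontinuers who stay in follow-up, are not in the SAP and are assumed.

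**2. The plan's own figure.** Expected MACE = 7500 × λ/(λ+μ) × [1 − mean of exp(−(λ+μ)t)]. With λ+μ = 0.1338, the mean over 2.5–5 years is (0.7157 − 0.5122)/0.3345 = 0.608. The result is 7500 × 0.2123 × 0.392 ≈ 624, which is the SAP's maximum. If half of those who drop out stayed in follow-up, the count would be 690; if all did, 756. The SAP's 10% is therefore loss from follow-up. Using 0.105 as a rate of stopping drug borrows a number and is an assumption.

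**3. Hand check of the mechanism.** Take 5 years for everyone, all discontinuers followed, and w = 30/365 = 0.082 year. The share of follow-up inside the event window at stopping hazard d is F(d) = [w + (1 − exp(−d(5 − w)))/d]/5.

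- F(0.10) = (0.082 + 3.885)/5 = 0.793
- F(0.15) = (0.082 + 3.479)/5 = 0.712

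Events scale with F while the time at risk is nearly the same in both arms, so the hazard ratio is multiplied by about 0.712/0.793 = 0.90. The exact large-sample Cox value is 0.900 (true 1.00) and 1.171 (true 1.30). With the arms reversed, 1.00 reads 1.111 and 1.30 reads 1.444.

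**4. Full calculation.** Solve for θ in ∫[e₁ − (e₀ + e₁)·θr₁/(r₀ + θr₁)]dt = 0. Here eⱼ is the density of countable MACE in arm j (up to last dose + 30 days) and rⱼ is the proportion in the risk set. Under last-contact censoring, rⱼ includes everyone still followed. Under matched censoring, rⱼ includes only those still inside the window. Stopping is independent of MACE risk, and discontinuers who do not stay leave when they stop drug. The reference arm stops at 0.105 per year. Each range covers both follow-up patterns and true hazard ratios of 1.0 and 1.3.

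| Other arm's stopping hazard | All stay | Half stay | None stay |
|---|---|---|---|
| 0.105 | 0% | 0% | 0% |
| 0.115 | −1.7 to −2.1% | −0.95 to −1.25% | 0% |
| 0.125 | −3.3 to −4.1% | −1.9 to −2.5% | 0% |
| 0.150 | −7.1 to −8.9% | −4.2 to −5.5% | 0% |

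In the last row, a true 1.30 reads 1.18–1.21 (all stay) or 1.23–1.25 (half stay), and a true 1.00 reads 0.91–0.93 or 0.94–0.96. Matched censoring returns the true value in every cell. Simulating 1.5 million subjects per arm in each scenario agrees to within about 0.2 percentage points.

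**5. Share of MACE excluded.** With equal stopping at 0.105 per year, the 30-day rule removes 17–21% of MACE if all stay and 9–12% if half do.

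**6. The 6.12.3 rate.** For stopping hazards of 0.10–0.25 per year and all or half staying, counting events to last dose + 30 days over days on treatment overstates the rate by 0.4–2.0%.

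**The case against.** The strongest objection is that the SAP leaves the date unstated and does not prescribe a biased one. The 6.12 rule covers subjects lost to follow-up or without an event, so it does not plainly reach a subject whose late MACE is excluded. The 6.6 sentence defines duration of participation for exposure summaries. A programmer might well censor at last dose + 30 days. This stands for subjects with a late MACE, but they are the minority: at 0.0284 per year, only 1 − exp(−0.0284 × 5) = 13% of discontinuers followed for 5 years would have one. For event-free discontinuers the 6.12 rule applies directly, and it gives last contact.

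Second, the size rests on undocumented inputs. The 10% in SAP 5.0 is loss from follow-up, which corresponds to the zero-bias column. The largest effect needs one arm to stop about 43% faster (0.150/0.105) with every discontinuer retained. This also stands: the figures show what could happen and do not forecast what will. But 3.2 provides for phone follow-up after stopping, so the zero-bias column is not what the design intends.

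Third, the 6.12.3 rates already give an on-treatment comparison on person-time that is largely free of this problem. They are descriptive, however, and do not correct the Cox estimate. The Fisher test in 6.4 would reveal an imbalance without removing its effect.

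Finally, censoring at last dose + 30 days is itself unbiased only if stopping is unrelated to MACE risk. That is a known limit of any on-treatment analysis. It is no reason to keep time at risk in which events are disallowed.

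**Conclusion.** The concern holds and should be fixed. The analysis in 6.12.1 has an event window without a matching end of risk time, and the only rule the SAP supplies biases the hazard ratio towards the arm that stops drug more. The bias is zero with equal stopping or with no follow-up after stopping. With all or half of discontinuers followed, it is about 1–2% for a gap of 1 point per year, 2–4% for 2 points and 4–9% for 4.5 points. These sizes depend on assumed stopping and retention rates and on stopping that is independent of MACE risk.

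The formal non-inferiority conclusion is untouched, since under 6.13 it rests on the primary analysis at the 75% look. The same gap does reach the CV-death analysis without deaths after discontinuation in 6.13, and mortality is the reason given there for continuing the trial. The denominator in 6.12.3 is a minor point: at most about 2%, and in the same direction in both arms.

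**What to change.** - **6.12.1:** State that this analysis counts first MACE through last dose + 30 days, and censors every other subject at the earliest of last dose + 30 days, last contact and study end. Say that this applies also to subjects whose later MACE is excluded, so that the last-contact convention in 6.6 does not govern them.
- **6.13:** State the window for CV death without deaths after discontinuation, and censor at its end. For all-cause death, refer to the window already given in 4.3 and 6.12.3 and censor at last dose.
- **6.12.3 (minor):** Accrue person-time over the same last dose + 30 days window that is used to count events.

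The cost is one or two sentences and one derived date. No new data are needed, and 6.6 already has a rule for estimating a missing last-dose date. The drawback is possibly informative censoring at discontinuation. The text should acknowledge it and point to the primary analysis, which keeps all follow-up, as the complement.
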